8.3 ADVERSE EVENTS AND SERIOUS ADVERSE EVENTS

Leave blank. Text should be included under the relevant subheadings below.

8.3.1 DEFINITION OF ADVERSE EVENTS (AE)

The FDA definition of an Adverse event is any untoward medical occurrence associated with the use of an intervention in humans, whether or not considered intervention-related (21 CFR 312.32 (a)).

8.3.2 DEFINITION OF SERIOUS ADVERSE EVENTS (SAE)

For this study, the following standard AE definitions are used:

Adverse event: Any unfavorable and unintended sign, symptom or disease temporally associated with the use of a medical treatment or procedure, regardless of whether it is considered related to the medical treatment or procedure.

Serious Adverse Event: Any AE that results in any of the following outcomes:

- Death
- Life-threatening event requiring inpatient hospitalization or prolongation of existing hospitalization
- Persistent or significant disability/incapacity

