- (5) Stable co-treatments (no hospitalizations or medication class changes in 2 months before enrollment). We will determine symptom and medication stability by best-estimate history with information from medical records;
- (6) Availability of a clinician (staff member, case manager, other mental health clinician) or close associate (family member, friend) with at least monthly contact who can be their informant – the purpose of informants is to complete the SLOF which is a rating scale measure of functional ability and the Cognitive Strategies which assess use of compensatory strategies in daily life;
- (7) Minimum level of functional impairment based on milestones, excluding participants who are full-time employed and financially responsible for their household.

Informants are nominated by the participant. As such, we are seeking a partial waiver of consent to reach out them to invite them to participate in the research. Following a standard phone script (see script), informants are invited to participate in the study and their nature of participation is detailed. If verbal consent is obtained, the questionnaires are administered by telephone at the same time as consent.

Our justification for a partial waiver of consent for informants is as follows: 1) The research component involves no more than minimal risk to subjects; 2) The research could not be carried out practicably without the waiver since the informant must be nominated by the participant; 3) The waiver will not adversely affect the rights and welfare of the subjects; and 4) Where appropriate, the subjects will be provided with additional information about their participation.

If a participant's nominated informant cannot be reached or declines participation, we will ask the participant to provide another informant. In the unlikely event that no informants agree to participate, the participant will not be dropped from the study.

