Monitoring and Responding to Suicidal Ideation or Clinical Worsening During Lab-Visits Our safety monitoring protocol is standardized and details these procedures, how they are recorded, and what the staff, facility, and investigator responsibilities are. Whereupon participants endorse active suicidal ideation on the Columbia Suicide Severity Rating Scale (CSSRS ≥ 2 ; up to past 1 month) or recent suicidal behavior (past up to past 3 months), the investigators at the corresponding site will be contacted. Additionally, a score exceeding 96 on the PANSS total (severe symptoms) or 30% increase in symptoms from prior would also lead to contacting the investigator. Research staff will document recent treatment contacts and the resources available to participant, including whether or not their clinical providers are aware of the participants current status. The investigator (licensed provider) or delegated licensed provider will perform an in-person evaluation to determine if immediate emergency services are necessary. Also, at each study visit and particularly during our final assessment with participants we will provide resources lists and support linkage to available services, crisis lines, and other resources. These efforts will be critical in the final study visit in order to mitigate against any potential loss of benefit of contact with research staff that might be experienced after the conclusion of study participation. Participants who have completed the protocol and who are no longer in the study will be allowed to and encouraged to reach out to study investigators in case of questions about community resources pertinent to mental health care or suicide prevention. These plans are developed to be in full accordance with the NIMH's Guidance on Conducting Research with Persons at Elevated Risk for Suicide.

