8.3.5 ADVERSE EVENT REPORTING

Adverse Event Definitions and Protocol: Any AE that is reported by the participant is noted by a study team member and will be reported to the PI and to the UCSD (or UTD or UM) Human Research Protection Office (HRPP) per their reporting policy and procedures. Any additional follow-up evaluations required by the event will also be evaluated by the PI and sent to HRPP per their reporting policy as well as to the DSMB. Any participant who develops an SAE will be followed-up through the resolution of the event and for one month thereafter. A log is kept of all AEs in a secure location at UCSD. Trained

research personnel will assess for any serious medical or psychological conditions that may require immediate medical attention or psychiatric treatment. Should attention be required, staff will provide these individuals with information about suitable referrals, including local hospitals, clinics, and/or relevant health-care and mental health professionals, and they the PIs will strongly encourage the individuals to follow up with these referrals. SAEs are reported to the DSMB, NIMH, and the HRPP within 24 hours

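### The SAE definition joins life-threatening status and hospitalization in one criterion, so some serious events would fall outside the expedited reporting rules

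*Combined protocol and SAP*

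**What the plan says.** Section 8.3.2 introduces its definitions as the standard ones. It defines an SAE as "Any AE that results in any of the following outcomes" and gives three bullets: death; "Life-threatening event requiring inpatient hospitalization or prolongation of existing hospitalization"; and "Persistent or significant disability/incapacity". No other section defines an SAE differently or lists hospitalization as a criterion of its own.

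Several rules then depend on SAE status:

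- **Section 8.3.5:** "SAEs are reported to the DSMB, NIMH, and the HRPP within 24 hours".
- **Section 8.3.6:** the PI reports any SAE to the sponsor immediately.
- **Section 8.3.4:** events are collected for 30 days after last participation if serious, and for 7 days if not.
- **Section 8.4.2:** an unanticipated problem that is an SAE goes to the IRB and the DCC/sponsor within 24 hours. Any other goes to the IRB within 10 days.

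AEs that are not serious still have a pathway. Section 8.3.4 puts every AE on a case report form. Under section 8.3.5 a participant-reported AE goes to the PI and to the "Human Research Protection Office (HRPP) per their reporting policy and procedures", and any follow-up evaluation is "sent to HRPP per their reporting policy as well as to the DSMB", with no deadline stated. Section 10.1.5 has the DSMB review AEs as well as SAEs, at meetings held semi-annually in the first year and annually after that.

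**The concern.** The word that links the two halves of the second bullet makes hospitalization a condition on the life-threatening event, not an alternative to it. Admission for relapse or suicidal ideation is a foreseeable event in adults with schizophrenia or schizoaffective disorder. Section 2.3.1 itself names the possible need to evaluate a participant for a higher level of care, and a theoretical increase in depression from the intervention.

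Staff who apply the text exactly would classify such an admission as a non-serious AE unless another bullet applied. What is at stake is the speed with which the DSMB, NIMH, the HRPP and the sponsor learn of it, and how long after the last visit such events are still collected. The trial is single-arm, section 10.1.6 marks clinical monitoring as not applicable, and section 10.1.1 gives unexpected significant risk as the only foreseeable ground for stopping. Prompt SAE reporting is therefore an important way for such a risk to surface.

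**Working it through.** The plan gives no figure to reproduce. The check is one of logic, followed by tracing the result through the reporting rules.

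**Step 1. Parse the bullet.** Let L = life-threatening, H = new inpatient admission, P = prolongation of an existing stay. The wording allows two readings:

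- (a) L and (H or P)
- (b) (L and H) or P

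Reading (c), L or H or P, is what two separate criteria would give.

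| Event (no death, no disability or incapacity) | (a) | (b) | (c) |
|---|---|---|---|
| New admission, not life-threatening | not SAE | not SAE | SAE |
| Life-threatening, no admission | not SAE | not SAE | SAE |
| Life-threatening, with new admission | SAE | SAE | SAE |
| Prolonged stay, not life-threatening | not SAE | SAE | SAE |

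The first two rows come out the same under (a) and (b), so the conclusion does not depend on which reading is taken.

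**Step 2. Allow for the other bullets.** The list needs only one outcome to be met. An event in the first two rows is still an SAE if it results in death or in persistent or significant disability or incapacity.

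**Step 3. Trace what changes for the events left out.**

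| Rule | If SAE | If AE only |
|---|---|---|
| Report to DSMB, NIMH, HRPP (8.3.5) | within 24 hours | PI, and HRPP under local policy; follow-up evaluations also to DSMB, no deadline |
| Report to sponsor (8.3.6) | immediate | no such rule |
| Collection after last participation (8.3.4) | 30 days | 7 days |
| Unanticipated problem (8.4.2) | 24 hours, IRB and DCC/sponsor | 10 days, IRB |

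The collection window shortens by 30 − 7 = 23 days. The deadline for an unanticipated problem lengthens from 1 day to 10.

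**Step 4. Compare with routine DSMB review.** Semi-annual meetings are about 52 / 2 = 26 weeks apart, and annual meetings 52 weeks. Participation lasts 16 weeks (synopsis). A participant could therefore finish the study before the next scheduled meeting reviews the event.

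**Step 5. Look for another provision that closes the gap.** The severity grading in section 8.3.3.1 does not, because it states that severe and serious are not the same thing. The procedure for suicidal ideation and clinical worsening in section 8.2 leads to contact with the investigator and an in-person evaluation "to determine if immediate emergency services are necessary". It sets no DSMB report and no reporting clock.

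**The case against.** The strongest reply is that this is a drafting slip with limited consequences. The list is presented as standard, and nothing in the protocol defends a narrower definition. Excluded events stay visible: they are recorded, followed to resolution, sent to the HRPP under local policy and reviewed by the DSMB. Protection of the participant in a crisis runs through section 8.2 and does not depend on the SAE label. All of this stands. It limits the consequence to lost expedited reporting and a shorter collection window, but it does not restore either.

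A second reply is that two bullets were run together when the PDF was converted to text. This cannot be wholly excluded, since one bullet in section 8.4.1 appears broken into two. But the second half of the disputed bullet begins in lower case and follows grammatically from the first, which makes a merge unlikely. The sponsor can settle it from the source file.

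A reader might infer more than the documents support in four ways:

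- **That these events can never be SAEs.** The disability/incapacity bullet remains open, and a relapse needing admission might be judged to meet it.
- **That most SAE reports would be missed.** The documents give no admission rate. Assuming 5% to 10% of 60 participants were admitted gives 0.05 × 60 = 3 to 0.10 × 60 = 6 people, but nothing shows how many of those admissions would be non-life-threatening and outside the other bullets. The share misclassified could lie anywhere from none to all.
- **That a planned result would be biased.** Section 9.4.4 confines the safety analyses to descriptive C-SSRS ideation rates and Negative Effects Questionnaire scores. SAE counts do not enter the go/no-go criteria in section 3, and depression is measured separately by the CDSS.
- **That the protocol elsewhere uses hospitalization as its marker of seriousness.** The entry criterion in section 5.1, "no hospitalizations or medication class changes in 2 months before enrollment", concerns stability of co-treatment, names medication changes equally, and does not bear on SAE classification.

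**Conclusion.** The point holds in limited form. As written, section 8.3.2 leaves two kinds of event outside the SAE definition unless death or persistent or significant disability or incapacity also results: a new admission that is not life-threatening, and a life-threatening event without admission. These events are not lost to oversight. They lose the 24-hour report to the DSMB, NIMH and HRPP, the immediate sponsor report, 23 days of post-study collection and, if they are unanticipated problems, the 24-hour deadline.

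The number of events affected cannot be derived from the documents, and the conclusion does not need one, since it follows from the wording alone. It rests on two assumptions: that the bullet reads in the source file as it does in the text, and that staff apply it literally.

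**What to change.** In section 8.3.2, replace the joint bullet with two: one for a life-threatening event, and one for inpatient hospitalization or prolongation of an existing hospitalization. Leave the reporting pathways in sections 8.3.4, 8.3.5, 8.3.6 and 8.4.2 as they are; they will then apply to both kinds of event without further edits. If the joint wording is intended, the sponsor should say so and justify it, because the section presents the list as standard.

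The cost is one line in a protocol amendment and possibly a few more expedited reports. No assessment, endpoint or analysis changes.

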8.3.3 CLASSIFICATION OF AN ADVERSE EVENT

Leave blank. Text should be included under the relevant subheadings below.

8.3.3.1 SEVERITY OF EVENT

All AEs will be assessed by the study clinician using a protocol defined grading system.

For safety, we will administer the Columbia Suicide Severity Rating Scale⁵⁰ (see *Suicide Protocol*). Since change in IA could theoretically lead to adverse experiences in some individuals (e.g., *greater awareness>depressed mood*), we will administer the Negative Effects Questionnaire (NEQ⁵¹) at follow-ups. These are descriptive in nature.

For adverse events (AEs) not included in the protocol defined grading system, the following guidelines will be used to describe severity.

- **Mild** – Events require minimal or no treatment and do not interfere with the participant’s daily activities.
- **Moderate** – Events result in a low level of inconvenience or concern with the therapeutic measures. Moderate events may cause some interference with functioning.
- **Severe** – Events interrupt a participant’s usual daily activity and may require systemic drug therapy or other treatment. Severe events are usually potentially life-threatening or incapacitating. Of note, the term “severe” does not necessarily equate to “serious”.]

8.3.3.2 RELATIONSHIP TO STUDY INTERVENTION

All adverse events (AEs) must have their relationship to study intervention assessed by the clinician who examines and evaluates the participant based on temporal relationship and his/her clinical judgment. The degree of certainty about causality will be graded using the categories below. In a clinical trial, the study product must always be suspect.

- **Related** – The AE is known to occur with the study intervention, there is a reasonable possibility that the study intervention caused the AE, or there is a temporal relationship between the study intervention and event. Reasonable possibility means that there is evidence to suggest a causal relationship between the study intervention and the AE.
- **Not Related** – There is not a reasonable possibility that the administration of the study intervention caused the event, there is no temporal relationship between the study intervention and event onset, or an alternate etiology has been established.

8.3.3.3 EXPECTEDNESS

The PI will be responsible for determining whether an adverse event (AE) is expected or unexpected. An AE will be considered unexpected if the nature, severity, or frequency of the event is not consistent with the risk information previously described for the study intervention

8.3.4 TIME PERIOD AND FREQUENCY FOR EVENT ASSESSMENT AND FOLLOW-UP

The occurrence of an adverse event (AE) or serious adverse event (SAE) may come to the attention of study personnel during study visits and interviews of a study participant.

All AEs including local and systemic reactions not meeting the criteria for SAEs will be captured on the appropriate case report form (CRF). Information to be collected includes event description, time of onset, clinician's assessment of severity, relationship to study product (assessed only by those with the training and authority to make a diagnosis), and time of resolution/stabilization of the event. All AEs occurring while on study must be documented appropriately regardless of relationship. All AEs will be followed to adequate resolution.

Changes in the severity of an AE will be documented to allow an assessment of the duration of the event at each level of severity to be performed. AEs characterized as intermittent require documentation of onset and duration of each episode.

Research staff will record all reportable events with start dates occurring any time after informed consent is obtained until 7 (for non-serious AEs) or 30 days (for SAEs) after the last day of study participation. At each study visit, the investigator will inquire about the occurrence of AE/SAEs since the last visit. Events will be followed for outcome information until resolution or stabilization.]

8.3.5 ADVERSE EVENT REPORTING

Adverse Event Definitions and Protocol: Any AE that is reported by the participant is noted by a study team member and will be reported to the PI and to the UCSD (or UTD or UM) Human Research Protection Office (HRPP) per their reporting policy and procedures. Any additional follow-up evaluations required by the event will also be evaluated by the PI and sent to HRPP per their reporting policy as well as to the DSMB. Any participant who develops an SAE will be followed-up through the resolution of the event and for one month thereafter. A log is kept of all AEs in a secure location at UCSD. Trained

research personnel will assess for any serious medical or psychological conditions that may require immediate medical attention or psychiatric treatment. Should attention be required, staff will provide these individuals with information about suitable referrals, including local hospitals, clinics, and/or relevant health-care and mental health professionals, and they the PIs will strongly encourage the individuals to follow up with these referrals. SAEs are reported to the DSMB, NIMH, and the HRPP within 24 hours

8.3.6 SERIOUS ADVERSE EVENT REPORTING

The study PI will immediately report to the sponsor any serious adverse event, whether or not considered study intervention related, including those listed in the protocol or investigator brochure and must include an assessment of whether there is a reasonable possibility that the study intervention caused the event. Study endpoints that are serious adverse events (e.g., all-cause mortality) must be reported in accordance with the protocol unless there is evidence suggesting a causal relationship between the study intervention and the event (e.g., death from anaphylaxis). In that case, the investigator must immediately report the event to the sponsor.

All serious adverse events (SAEs) will be followed until satisfactory resolution or until the site investigator deems the event to be chronic or the participant is stable.

8.3.7 REPORTING EVENTS TO PARTICIPANTS

Not Applicable

8.3.8 EVENTS OF SPECIAL INTEREST

Not Applicable

8.3.9 REPORTING OF PREGNANCY

Not Applicable

8.4 UNANTICIPATED PROBLEMS

Leave blank. Text should be included under the relevant subheadings below.

8.4.1 DEFINITION OF UNANTICIPATED PROBLEMS (UP)

The Office for Human Research Protections (OHRP) considers unanticipated problems involving risks to participants or others to include, in general, any incident, experience, or outcome that meets all of the following criteria:

- Unexpected in terms of nature, severity, or frequency given (a) the research procedures that are described in the protocol-related documents, such as the Institutional Review Board (IRB)-

- approved research protocol and informed consent document; and (b) the characteristics of the participant population being studied;
- Related or possibly related to participation in the research (“possibly related” means there is a reasonable possibility that the incident, experience, or outcome may have been caused by the procedures involved in the research); and
- Suggests that the research places participants or others at a greater risk of harm (including physical, psychological, economic, or social harm) than was previously known or recognized.

8.4.2 UNANTICIPATED PROBLEM REPORTING

The investigator will report unanticipated problems (UPs) to the reviewing Institutional Review Board (IRB). The UP report will include the following information:

- Protocol identifying information: protocol title and number, PI’s name, and the IRB project number;
- A detailed description of the event, incident, experience, or outcome;
- An explanation of the basis for determining that the event, incident, experience, or outcome represents an UP;
- A description of any changes to the protocol or other corrective actions that have been taken or are proposed in response to the UP.

To satisfy the requirement for prompt reporting, UPs will be reported using the following timeline:

- UPs that are serious adverse events (SAEs) will be reported to the IRB and to the DCC/study sponsor within 24 hours of the investigator becoming aware of the event.
- Any other UP will be reported to the IRB within 10 days of the investigator becoming aware of the problem.

8.4.3 REPORTING UNANTICIPATED PROBLEMS TO PARTICIPANTS

Not Applicable

9 STATISTICAL CONSIDERATIONS

9.1 STATISTICAL HYPOTHESES

The statistical hypotheses are that adherence will exceed the criterion of 75% and that there will be a pre-post change in the VLMT, METER and WCST tasks that will exceed that of 0.5 Cohen’s d with the baseline sample wide standard deviation serving as the denominator.

9.2 SAMPLE SIZE DETERMINATION

We used the Monte Carlo simulation capabilities of Mplus version 8.4⁵² to perform our power analyses. To determine our levels of power to detect changes in IA for the list-learning task or emotion recognition tasks equivalent to $d = |0.50|$ for R61 Aim 1, we specified three-level models with 1000 replications each wherein trials ($t = 18$) were nested within weeks ($w = 8, 12, \text{ or } 16$) that were further nested within persons ($n = 60$ or 48 in the case of 20% attrition). These models were similar to Figure 1 with the exception that changes in IB and IA at Level 3 were not regressed on intervention condition. As can be seen in Table 1, our power levels were excellent (i.e., $> .90$) across all combinations of sample size and week size, ranging from .91 for detecting changes in IA of $d = -0.50$ at 8 weeks with 48 participants to .97 for detecting changes in IA of $d = 0.50$ at 16 weeks with 60 participants.

To determine our levels of power to detect transfer-of-training for R61 Aim 1 and optimal dosing for Aim 2, we again specified three-level models with 1000 replications each wherein trials ($t = 18$) were nested within weeks ($w = 8, 12, \text{ or } 16$) that were further nested within persons ($n = 60$ or 48 in the case of 20% attrition). However, we modified these models such that they included an additional Truth and Bias model for the WCST transfer of training target at Level 2 that had a change in IB of $d = -0.50$ across the weeks. To reflect the fact that this in-laboratory tasks would only be measured at 0, 4, 8, 12, and 16 weeks, we specified that these measurements should have 62.5% missing data in the simulations (e.g., only completing 3 out of 8 weeks). As can be seen in Table 2, we should have more-or-less adequate levels of power to detect a change in IB for the in-lab assessment at 16 weeks with 48 participants (power = .77) and adequate power to detect a change in IB for the in-lab assessment at 12 and 16 weeks with 60 participants (power = .78 and .83, respectively).

To determine our levels of power to detect exploratory predictors of changes in IA for the list-learning and emotion recognition tasks, as well as to detect the effects of changes in IA for the list-learning task and emotion recognition on functional outcomes, we modified the original models for R61 Aim 1 such that we either regressed changes in IA for the mobile tasks task on a predictor, or regressed a functional outcome on changes in IA, respectively.

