3 OBJECTIVES AND ENDPOINTS

In this pilot project, there are two objectives. Firstly, we will evaluate, in an open trial, whether iTEST is acceptable, indexed by adherence, and engages IA as a target, indexed by improved IA on trained

tasks and transfer on an untrained task in a different domain. Secondly, we will evaluate optimal dosing of the intervention, by whether go/no-go criterion for improvement is achieved at 8, 12, or 16 weeks.

Our go/no go criteria are threefold: 1) To demonstrate feasibility, the average adherence must be equal to or exceed 75%, 2) To show target engagement, we require a significant improvement in IA ($d > .50$) on both trained tasks, and 3) To show transfer of training, we require significant improvement in IA ($d > .50$) on the untrained Wisconsin Card Sorting Task. Criteria may be met prior to 16 weeks, at weeks 8 or 12 (Note: all participants continue through 16 weeks).

OBJECTIVES	ENDPOINTS	JUSTIFICATION FOR ENDPOINTS
Primary		
To evaluate the acceptability and preliminary impact on our target, IA	
Adherence defined as the ratio of completed mobile prompts completed divided by the number possible – 75% is the criterion
 
Clinically significant (Cohen's $d > 0.5$) improvement in trained introspective accuracy as measured by IA on our Verbal Learning and Memory Test and Mobile Electronic Test of Emotion Recognition tasks. These are administered 6x per week for 16 weeks.
 
Clinically significant (Cohen's $d > 0.5$) improvement in untrained introspective accuracy (global resolution score) on the WCST. The WCST is administered at baseline, 8, 12 and 16 weeks.
	
Adherence at a level of 75% is generally accepted in mobile intervention studies such as this
 
The reason that trained tasks are part of our Go/No Go criteria is because lack of improvement on trained tasks would call into question the ability of iTEST to modify IA, and would indicate need for program revisions. IA is calculated as the discrepancy (absolute) between each trial's correct performance from that estimated by the participant, which is nested within sessions and weeks.
 
An additional Go/No Go component is transfer of training to an untrained task-based measure of IA, the Meta-Cognitive Wisconsin Card Sorting Test¹³. IA on this task is also associated with functioning and improvement on this task would support that iTEST

OBJECTIVES	ENDPOINTS	JUSTIFICATION FOR ENDPOINTS
		leads to generalized improvement in IA.
Secondary		

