4.1 OVERALL DESIGN

Hypothesis:

Target Engagement Hypothesis: Participants' adherence and average changes in IA for the mobile tasks and pre- post differences in meta-cognitive WCST will meet or exceed our go/no go criteria

Optimal Dosing: Target engagement may occur prior to 16 weeks, at week 8 or 12. We would select the optimal dose for the R33 is determined by selecting the earliest assessment point that reaches go/no go criteria - all participants receive the same dose

Phase of the trial, if applicable: This is a pilot behavioral intervention and so study phases are somewhat difficult to apply but would be mostly consistent with a Phase Ib study that is investigating acceptability and a preliminary effect in a diseased population

Design of Trial: Single arm, unblinded, open pilot trial.

Methods used to minimize bias: Measures are standardized and accepted endpoints and the sample has few exclusion criteria for entry

Dosing: All participants receive the same dose. We will investigate the point at which (among 8, 12, and 16 weeks) go/go criteria are met.

Intervention groups: This is a single arm trial and the duration of the intervention is 16 weeks.

Sites: There will be 2 sites – UCSD is the prime site and University of Texas at Dallas will be the secondary site with their own IRB.

Study Intervention: iTEST

Interim Analysis: No interim analysis is planned

Stratification: None

Name of sub-studies, if any, included in this protocol: None

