9.4 STATISTICAL ANALYSES

9.4.1 GENERAL APPROACH

[figure not shown]
As this is a pilot study, there is no formal SAP

Since our analyses focus on clinically significant magnitude of effects or achievement of thresholds, significance testing is not relevant

We will use Multilevel Structural Equation Modeling (MLSEM) with three levels to estimate changes in levels of Introspective Accuracy (IA) across trials (level 1) and/or weeks (level 2) within persons (level 3). Figure 1 presents an example three-level model wherein changes in IA for the *Variable Length Memory Test* (VLMT) list learning and *Mobile Electronic Test of Emotion Recognition* (METER) emotion recognition are simultaneously estimated. Given the relatively large number of random effects, we will use Bayesian

estimation rather than maximum likelihood estimation for the analyses⁵³. Although some task or ability domains will not be measured at every trial or every week, specifying trial as Level 1 (e.g., for IA on mobile task) and week as Level 2 (e.g., for WCST) will still enable us to estimate changes in IA for these domains.

Figure 1. Three-Level Multilevel Structural Equation Model

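### The power in Section 9.2 is for detecting a change of d = 0.50, not for meeting the go rule, which at that true effect is met about half the time per task and less often on all three

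*Combined protocol and SAP*

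**What the plan says.** Section 9.2 plans for a change of d = 0.50 with 60 participants, or 48 after 20% attrition. For the trained tasks it concludes that "our power levels were excellent (i.e., $> .90$) across all combinations of sample size and week size". The lowest value it reports is .91 (48 participants, week 8) and the highest is .97 (60 participants, week 16). For the WCST it simulates a task "that had a change in IB of $d = -0.50$ across the weeks" and reports power of .77 (48 participants, week 16), .78 (60, week 12) and .83 (60, week 16). It states neither the null hypothesis nor alpha.

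The decision rule is in Section 3: mean adherence of at least 75%; "we require a significant improvement in IA ($d > .50$) on both trained tasks"; and the same on the untrained WCST. Section 9.1 says the change must exceed 0.5, with the baseline SD as denominator. Section 9.4.1 judges this by inspecting the standardized differences at weeks 8, 12 and 16, and says that "significance testing is not relevant". Section 4.1 chooses the duration for the R33 trial by "selecting the earliest assessment point that reaches go/no go criteria".

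No section gives the probability of meeting the go rule.

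**The concern.** The power figures and the decision answer different questions. The figures ask whether a true change of 0.50 would be detected. The decision asks whether three estimates all exceed 0.50. With the planning effect on the pass mark, an unbiased estimate falls below it about half the time, and a larger sample does not change that.

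Section 1.2 makes the randomized R33 trial depend on this decision. A no-go after power described as excellent would naturally be read as failed target engagement, although a true effect of the planned size would often produce it. In the other direction, accepting the earliest of three assessments gives an effect below 0.5 more than one chance to pass. The plan quantifies neither error.

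Two smaller points belong here. The WCST power is for a change in IB (bias), whereas the Section 3 criterion is for IA. And Section 3 asks for significant improvement, whereas Section 9.4.1 sets significance testing aside.

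**Working it through.** **Inputs from the documents.** Planning effect d = 0.50; n = 60, or 60 × 0.8 = 48; threshold 0.50 on three tasks; visits at weeks 8, 12 and 16; baseline-SD denominator.

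**Assumed, because the documents do not give them.** Two-sided alpha .05; between-task correlation ρ of 0 to 0.8, equal for all pairs; between-visit correlation τ of .5 to .9; pre-post correlation r, taken as .5 unless stated, at which the SD of change equals the baseline SD. The three tasks must pass at the same visit.

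**1. The plan's own figure.** The Mplus simulation cannot be rerun, since its variance components are not given. A one-sample t test of zero change has noncentrality d√n:
- n = 48: 0.5 × √48 = 3.46, power .924 (stated .91)
- n = 60: 0.5 × √60 = 3.87, power .968 (stated .97)

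The stated values are therefore about what a test of zero change gives. Power for exceeding 0.5 could not be above .90 when the true value is 0.5.

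**2. One task, true d = 0.5.** Simulating pre and post scores with the estimated baseline SD as denominator, P(estimate > 0.5) is .51 to .52 for n = 48 or 60 and r from .3 to .9.

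**3. All three tasks, one visit, true d = 0.5.** With each estimate centred on the threshold, P = 1/8 + (3/4π) × arcsin(ρ):

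| ρ | P(all three > 0.5) |
|---|---|
| 0 | .125 |
| 0.3 | .198 |
| 0.5 | .250 |
| 0.8 | .346 |

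**4. All three tasks at any of the three visits.** Simulation of nine correlated normal estimates (three tasks by three visits), n = 60. On the linear path, d is 0.5 × 8/16 = 0.25 at week 8, 0.5 × 12/16 = 0.375 at week 12, and 0.5 at week 16. Each cell gives the range over τ of .5 to .9.

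| ρ | d = 0.5 at every visit | d linear to 0.5 at week 16 |
|---|---|---|
| 0 | .20-.28 | .13 |
| 0.3 | .29-.40 | .20-.21 |
| 0.5 | .35-.47 | .25-.26 |
| 0.8 | .45-.59 | .35-.37 |

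Adherence is not included and can only reduce these values.

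**5. A sub-threshold effect, true d = 0.4 at every visit, n = 60, τ = .7.** The standard error is √(2(1 − r)/n). At r = .5 it is √(1/60) = .129, so z = 0.1/.129 = .775.
- One task: .22 at week 16, .37 at any visit.
- All three tasks (ρ = .5): .06 at week 16, .12 at any visit.

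The level depends on r. At r = .7 the standard error is .100, z = 1.00, and the one-task week-16 figure is .16. At r = .9 it is .058, z = 1.73, and the figure is .04.

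**The case against.** Several replies have force.

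- **A single visit is not the rule.** A reader might take 13-35% as the chance of go. Sections 3 and 4.1 let the criteria be met at week 8, 12 or 16, so that range is for one visit only, and the any-visit figures reach about 59%.
- **The plan does not promise a 90% chance of go.** A reader might infer this from the word excellent. Section 9.2 claims power above .90 only for the trained tasks and calls the WCST figures adequate or more-or-less adequate. Even against zero change, its best figures multiply to .97 × .97 × .83 = .78 if the tasks are independent.
- **No single true effect guarantees 80%.** It is tempting to say that d must be about 0.7. At one visit with r = .5 the value is about 0.65-0.69 for n = 60 and 0.67-0.71 for n = 48. It falls with a higher pre-post correlation or with three visits allowed, so the documents support no fixed number.
- **The zero null is inferred.** The stated .91 and .97 differ in weeks as well as n, and a t test has no term for weeks. The match is suggestive. The stronger argument is that a threshold of 0.5 cannot have such power at d = 0.5.
- **Significant may mean magnitude.** The endpoint table in Section 3 speaks of clinical significance at d > 0.5, and Section 9.4.1 uses the same idea. This is a matter of wording and not a substantive conflict.
- **It is a single-arm pilot.** True, but its purpose is the go/no-go decision, so the behaviour of that rule is the design property that matters most.

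None of these supplies the missing probability of go or raises it near the quoted power at the planning effect.

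**Conclusion.** The concern holds in this form. The arithmetic in Section 9.2 is not shown to be wrong: its trained-task figures are close to those from a test of zero change. But they do not describe the decision the trial will make. At a true d of 0.5 each task passes about half the time whatever the sample size. The joint chance is about 13-35% at one visit, and over the three visits about 20-59% (constant effect) or 13-37% (linear rise), before adherence. Of the 24 any-visit combinations run (two effect paths, four values of ρ, three of τ), only two exceed 50%. At d = 0.4, allowing any visit roughly doubles the joint chance of passing, from .06 to .12 under the stated correlations.

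That a pass at the planning effect is about even per task needs no correlation assumption. The joint and any-visit ranges do rest on the assumed correlations and effect path. The documents do not support a single figure for the chance of go.

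**What to change.** 1. In Section 9.2, label the existing figures as per-task power against zero change, state the null and alpha, and say that the WCST figures are for IB whereas the criterion is for IA.
2. Add the operating characteristics of the actual go rule, all criteria jointly including adherence: P(go) at each visit and at any visit, for true d from about 0.3 to 0.8, n = 60 and 48, with the baseline-SD denominator and stated ranges for the pre-post, between-task and between-visit correlations.
3. Report each d with its 95% credible interval. Section 9.4.1 already plans Bayesian estimation.
4. State in Section 3 that significant means magnitude (d > .50), to agree with Section 9.4.1.
5. Report whether criteria met at week 8 or 12 are still met at later visits. All participants continue to week 16, so the data will exist. This is reporting only and adds no new rule for choosing the duration.

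The cost is a short simulation and some wording, with no extra participants or visits. The downside is that the stated figures become less favourable.
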